development of a robust, clinically feasible rsfMRI data analysis pipeline, this study is expected to result in improved understanding of the functional reorganization that takes place during and after intervention.

4. Study Procedures

- Study design, including the sequence and timing of study procedures (distinguish research procedures from those that are part of routine care).

This will be an early phase 1 (phase 0) clinical trial. Specifically, the study will be performed as a randomized, parallel group trial to determine if the amount of changes in brain functional connectivity outcome measures (i.e., between network connectivity) is significantly different between the group of patients that perform FES cycling and another group of patients that perform passive (sham) cycling.

Patients of the International Center for Spinal Cord Injury (ICSCI) at the Kennedy Krieger Institute (KKI) will be identified as meeting the inclusion criteria by reviewing the medical records held by the ICSCI. Once the patient consents by signing the consent form, official screening of subjects will be performed. Subjects will be randomized into 2 groups: FES cycling (Group 1; n=24) and passive cycling (Group 2; n=24). The patients will undergo either an FES cycling or a passive cycling sessions for 4 weeks, 3 times a week. **Acquisition of rsfMRI measures:** MRI will be performed on all participants at the beginning (prior to cycling sessions) and at the end of the 2nd and 4th weeks of the intervention program. **Acquisition of clinical measures:** ISNCSCI and SCIM (Spinal Cord Independence Measure) evaluations will be performed to coincide with the dates of MRI acquisitions, to determine the neurological level and the degree of sensory and motor impairments. Detailed study timeline can be found in Figure 1.

[figure not shown]

Figure 1. Study Timeline.

- SCI patients assigned to FES cycling group will take part in the following evaluations:
 - Medical chart review / MRI screening questionnaire
 - FES cycling trial
 - Neurological evaluation (ISNCSCI – more commonly known as ASIA exam)
 - Functional evaluation (SCIM)
 - MRI

Date: 4.14.2023

Principal Investigator: [name].

Application Number: IRB000182576

E1: FES cycling

- SCI patients assigned to passive cycling group will take part in the following evaluations:
 - A: Medical chart review / MRI screening questionnaire
 - B2: Passive cycling trial

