Patients who are assigned to the passive cycling group will act as a non-treatment group. By comparing the outcome measures of the FES- and Passive-cycling groups, we will be able to determine whether it is the active neuromuscular conduction triggered by FES that leads to alteration in cortical functional connectivity, as opposed to a simple movement of muscles. Physiological effects of FES cycling require treatment for several months. Our proposed study is short (4 weeks). And as such, we expect minimal neurological differences between the FES and passive cycling groups. In contrast, we expect early, observable, and detectable differences in cortical functional connectivity between the FES and passive cycling groups.

- f. Definition of treatment failure or participant removal criteria.

Subjects may withdraw from the study at any time for any reason. Additionally, a subject may be removed from the study for any of the following reasons:

- The subject experiences a medical emergency that necessitates discontinuation of therapy
- The subject experiences a serious adverse event that is judged to be likely related to the assigned treatment group or is of severity that warrants discontinuation of assigned treatment.
- For any medical reason at the discretion of the investigator.
- Subject is not compliant: participants who miss more than 3 sessions of cycling for the duration of the study.
- Subject becomes pregnant.

- g. Description of what happens to participants receiving therapy when study ends or if a participant’s participation in the study ends prematurely.

Upon completion of the study, participants will be referred back to their treating SCI specialist who will be made aware of the treatment and follow-up. The same protocol will be followed for patients who terminate the study early. In the event of discontinuation due to adverse event, participants will be followed by the PI and a medical supervisor of the study ([name]) until resolution or stabilization of their adverse condition and then referred back to their treating SCI specialist.

5. Inclusion/Exclusion Criteria

Only subjects who agree voluntarily to participate in these procedures after they have been fully informed will be included, and who can comprehend the nature of these procedures can participate. Also, their actual involvement will be discussed with them repeatedly to assure adequate knowledge. Subjects will be

Date: 4.14.2023

Principal Investigator: [name].

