- c. Justification and safety information if non-FDA approved drugs without an IND will be administered.

Date: 4.14.2023

Principal Investigator: [name].

Application Number: IRB000182576

N/A

7. Study Statistics

a. Primary outcome variable.

Type	Name	Time Frame	Brief Description
Primary	International Standard of Neurological Classification for Spinal Cord Injury (ISNCSCI)	baseline, mid-intervention, post-intervention	Developed by the American Spinal Injury Association (ASIA) as a universal classification tool for spinal cord injury (SCI). The classification tool involves a sensory and motor examination to determine the neurological level of the injury and whether the injury is complete or incomplete. The tool also provides sensory and motor scores of upper and lower body, as well as right and left of the body. The ISNCSCI defines neurological level as the most caudal level at which sensory and motor function are intact. The completeness of the injury is graded according to the ASIA Impairment Scale (ISNCSCI).
Primary	Resting state fMRI functional connectivity	Baseline, mid-intervention, post-intervention	RsfMRI functional connectivity is defined as the temporal dependency of neuronal activation patterns (represented by the blood oxygenation level dependent (BOLD) signal time courses as measured using rsfMRI) of anatomically separated brain regions. There are number of methodologies one can use to characterize the degree and type of rsfMRI functional connectivity. One example is between-network-connectivity (BNC), which is defined as the degree of correlation between two time courses obtained from a pair of brain regions. Summary statistics of BNC (e.g., mean, variance), as well as the dynamic properties of BNC (e.g., dynamic functional connectivity) can be used to further summarize the characteristics of the functional connectivity in SCI population.
Primary	RsfMRI brain parcels	Baseline, mid-intervention, post-intervention	RsfMRI functional connectivity can also be used to identify functionally homogeneous brain regions, or parcels of the brain. The parcels' center of mass, spatial maps, average and variance of the BOLD signal time courses within the parcels can be used to characterize brain functional organization.

b. Secondary outcome variables.

Type	Name	Time Frame	Brief Description

Date: 4.14.2023

Principal Investigator: [name].

Application Number: IRB000182576

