Preliminary study: In this preliminary study, we hypothesized that BNC of sensorimotor and visual networks will correlate with the total ISNCSCI score, and performed the study to determine the feasibility of a larger population study. Twelve SCI patients were recruited, and the relationship between the ISNCSCI score and BNC measurements was examined. ISNCSCI sub-scores were first obtained, which were: total upper and lower body motor scores, and total sensory score. The sum of the three scores provided the total ISNCSCI scores. Analysis of the data consisted of preprocessing, PCA, and GICA, and total of 14 intrinsic functional components were identified. BNC between the sensorimotor and visual networks were computed, and plotted against the total ISNCSCI scores. Linear regression analysis was performed to find the best linear fit for the plots. Stronger BNC between the sensorimotor and visual networks was associated with lower total ISNCSCI scores ($R^2=0.35$, $p = 0.04$; [Figure 2](#)[Figure 2](#)). In other words, patients with greater degree of physical impairment tended to have stronger functional connectivity between the sensorimotor and visual networks, suggesting compensatory plastic cortical changes that are related to clinical presentation of the patients. Overall, BNC measures showed good correlations with the total ISNCSCI scores, supporting our hypothesis.

Between network connectivity (BNC) measurements from the above preliminary study provided means, standard deviations, and correlation coefficients for 12 SCI patients. A power analysis¹ revealed that a sample size of 24 subjects will be required to achieve 80% power at an alpha of 0.018; the alpha level was lowered with the correction for multiple comparisons in mind. We will therefore recruit a total of 48 patients. At this point, we do not have enough information about the variability of the BNC in response to the FES to perform a more stringent power analysis. We will use the data in the first 24 SCI subjects recruited to the study to assess the degree of variability in the metric. Based upon these estimates, we will then perform a power analysis to determine how many more subjects will need to be enrolled to assess the significance of our findings.

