The spatial maps of ICA- and SCA-derived brain parcels will be compared across groups. First, the participant-specific sensory and motor brain parcels will be converted to z values, so image intensities reflect the degree to which the parcel is present in each participant's data. The brain parcels will be combined in a second-level random effects analysis using a two sample t-test in SPM8. Voxels that contributed unequally to the parcels across groups will be identified using a liberal voxel-wise p value of 0.01 and a cluster-level p value of 0.05 corrected for multiple comparisons². The between network connectivity (BNC) between sensory and motor parcels will be calculated using Pearson's correlation coefficient between pairs of participant specific motor and sensory brain parcels³. Pairwise-correlations will be converted to Z-scores using Fisher's transformation, and the BNC across groups will be compared using two-sample t tests and adjusted p-values using a false discovery rate correction. Next, we will investigate whether sensory and motor BNC measured at week 2 of cycling program are related to motor and sensory International Standards for Neurological Classification of Spinal Cord Injury (ISNCSCI) scores measured at week 4, using a multivariate linear regression model analysis. Finally, the longitudinal inter- and intra-subject reproducibility of the ICA- and SCA-derived brain parcels will be assessed using intra-class correlation coefficient (ICC).

d. Early stopping rules.

[figure not shown]

Figure 2. Correlations between sensorimotor-visual BNC measurements and total ISNCSCI scores in SCI patients suggest a compensatory plastic cortical changes that are related to clinical presentation of the patients. Patients with lower ISNCSCI score showed larger degree of functional connectivity between the sensorimotor and visual networks.

Date: 4.14.2023

Principal Investigator: [name].

Application Number: IRB000182576

The principal investigator may discontinue the study if the interim statistical analysis as described above indicates that the number of subjects required for this trial exceeds 50.

Patients may withdraw from the study at any time for any reason. Any investigator may discontinue a patient for any of the following reasons:

- The subject experiences a medical emergency that necessitates discontinuation of therapy

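### Three outcome families are all primary, their imaging metrics are left open, and no rule controls error across them

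*Combined protocol and SAP*

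**What the plan says.** **Section 7a.** Three rows carry the label primary, each measured at baseline, mid-intervention and post-intervention.

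- ISNCSCI: "The tool also provides sensory and motor scores of upper and lower body, as well as right and left of the body". None of these scores is chosen.
- Connectivity: "There are number of methodologies one can use to characterize the degree and type of rsfMRI functional connectivity". BNC is then offered as one example, and its mean, variance and dynamic properties are also allowed.
- Parcels: centre of mass, spatial maps, and the average and variance of the signal are all allowed.

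**Section 7c, analyses.** BNC is the Fisher-transformed Pearson correlation between sensory and motor parcels, and "the BNC across groups will be compared using two-sample t tests and adjusted p-values using a false discovery rate correction". No false discovery rate level is given. For the parcels, "The spatial maps of ICA- and SCA-derived brain parcels will be compared across groups", with a corrected cluster-level threshold of 0.05. A regression then relates week-2 BNC to week-4 motor and sensory ISNCSCI, with no significance level stated.

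**Section 7c, sample size.** 24 subjects for 80% power at 0.018, with the remark that "the alpha level was lowered with the correction for multiple comparisons in mind".

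**Section 4, study design.** The randomised question is singular: "to determine if the amount of changes in brain functional connectivity outcome measures (i.e., between network connectivity) is significantly different between the group" given FES cycling and the group given passive cycling.

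**Section 4e.** "Physiological effects of FES cycling require treatment for several months", and over the 4 weeks of this study "we expect minimal neurological differences between the FES and passive cycling groups". Aim 2 in section 2, by contrast, takes week-4 ISNCSCI change as the quantity that early BNC change should predict.

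**The concern.** A primary outcome fixes in advance which result decides the trial. Here the reader cannot tell which score, metric, parcellation, visit or contrast that is. The corrections in section 7c each act inside one analysis and do not link the three families. The one sign of a joint allowance, the level of 0.018, appears only in the sample size paragraph. It comes with no list of the comparisons it covers and does not return as a test level.

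At stake is what a significant primary result would mean. If any of several tests can supply it, its error rate is not 5%, and because the number of tests is undefined the true rate cannot be stated. That weakens a biomarker claim even in a small early study.

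A related tension concerns ISNCSCI. Section 4e expects little neurological difference between the arms at 4 weeks, while Aim 2 needs week-4 ISNCSCI change to predict. If FES produces little change by then, there is little treatment-related variation for BNC to track.

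**Working it through.** **1. The plan's own figure.** Inputs from section 7c: R² = 0.35 in 12 patients, 80% power, level 0.018. The test and the effect behind the 24 are not named. I assume a test of one correlation with the only effect printed, |r| = √0.35 = 0.592.

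- Pilot p-value: t = √(0.35 × 10 / 0.65) = 2.32 on 10 degrees of freedom, p = 0.043, which agrees with the printed 0.04.
- Fisher z: n = ((z for the level + z for power) / atanh r)² + 3. Two-sided: ((2.366 + 0.842) / 0.680)² + 3 = 25.2, so 26. One-sided: 21.7, so 22.
- Bivariate-normal simulation, two-sided: power 78.8% at n = 24 and 81.0% at n = 25. A fixed-predictor regression F test needs 23.

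All are within two patients of 24, so the figure is consistent with one correlation test at 0.018. On this reading, the level was applied to a cross-sectional correlation of sensorimotor-visual BNC with total ISNCSCI score, which is not an analysis listed in section 7c.

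**2. What 0.018 could stand for.** 0.05 / 0.018 = 2.78, not a whole number. A Bonferroni split over three tests gives 0.05 / 3 = 0.0167, and a Šidák split gives 1 − 0.95^(1/3) = 0.0170. So 0.018 is close to a three-way split but is not one exactly.

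**3. Error across three families, one test each.** Assumption: every family is tested once, at the same level.

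| Level per family | Independent tests | Bound under any dependence |
|---|---|---|
| 0.05 | 1 − 0.95³ = 14.3% | 3 × 0.05 = 15% |
| 0.018 | 1 − 0.982³ = 5.3% | 3 × 0.018 = 5.4% |
| 0.0167 | 1 − 0.9833³ = 4.9% | 5% |

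Counting the BNC family as one test at 0.05 is fair if its false discovery rate is set at 0.05: when no null hypothesis is false, the false discovery rate equals the chance of any false positive in that family. Correlated families would bring the 14.3% down. More than one test per family, which section 7a permits, would push it up.

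**4. Which part of section 7c reaches which family.**

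| Family in 7a | Analysis in 7c | Error control |
|---|---|---|
| Connectivity | BNC, two-sample t tests between arms | False discovery rate within these tests, level not stated |
| Parcels | Map comparison between arms, ICA and SCA | Cluster-level 0.05 within the comparison |
| ISNCSCI | Outcome of the week-2 BNC regression | None stated |
| All three jointly | None | None |

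**The case against.** The strongest reply is that multiplicity was considered. The planning level was lowered for it, and three tests at 0.018 would give 5.3%, close to the usual 5%. False discovery rate and cluster corrections are in place. Section 7c also narrows section 7a by defining one BNC calculation and one test, and the sentence about several methodologies sits in a descriptive column. The study is called early phase 1 (phase 0), where strict family-wise control is not normally demanded.

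Much of this stands. It would be wrong to say that the plan has no multiplicity control, and 14% is not its computed error rate: section 7c states 0.05 only as the cluster threshold. But the controls stop at the edge of each analysis, 0.018 is tied to no test, and section 7a still lets other metrics count as primary. The plan also uses primary outcomes, 80% power and significance testing. If the study is meant to be exploratory, it should say so.

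Three stronger readings are tempting, and the documents do not support them.

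- *ISNCSCI is a between-arm primary that is bound to fail.* Section 7c contains no between-arm ISNCSCI test, and section 4e says the expected differences are minimal, not absent.
- *Each ICA and SCA map at each follow-up visit adds a further independent test.* The two parcellations come from the same scans, so independence does not hold, and section 7c names no visit for the map comparison.
- *Power for Aim 2 can be computed by shrinking the pilot correlation for unreliable ISNCSCI change.* The documents give no reliability. The pilot correlation was observed, so it already contains measurement error, and it relates levels rather than changes and a different network pair.

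**Conclusion.** The point holds. Section 7a names three primary families with open imaging metrics and no key score, visit or contrast. Section 7c controls error only within the BNC tests and within the map comparison, and 0.018 governs no stated analysis. The size is illustrative: about 14% (at most 15%) for one test per family at 0.05, against about 5.3% at 0.018. It rests on one test per family and, for the 14%, on independence.

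The ISNCSCI matter is a tension between section 4e and Aim 2, not a contradiction. A small mean difference between arms does not exclude variation between patients in 4-week change. The documents give no standard deviation for that change, so the consequence cannot be quantified. This should be corrected, but it is a matter of definition and does not undermine the design.

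**What to change.** **Preferred.** In section 7a, name a single primary: the between-arm difference in change from week 0 to week 2 in the sensory-motor BNC already defined in section 7c, from one stated parcellation, tested two-sided at 0.05. This matches the question in the study design section. Section 7c refers to pairs of parcels, so also state how they reduce to one value per patient (one named pair, or the mean Fisher-z value).

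Keep the Aim 2 regression as the key secondary, since prediction is the study's stated goal. Word it in changes, as Aim 2 does (week-2 BNC change against week-4 motor and sensory ISNCSCI change), and state the order of testing, including which of motor and sensory comes first. Label parcel maps, other metrics, the other parcellation and week-4 imaging contrasts secondary or exploratory. Add a sentence reconciling section 4e with Aim 2.

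**Alternative.** Keep up to three primary tests, list them, and carry a split level into section 7c: 0.05 / 3 = 0.0167 each. Using 0.018 for three would slightly exceed 5%.

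**Cost.** No new data, visits or patients; only protocol and SAP wording.

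- Under the first option the other outcomes lose primary status, and under an ordered scheme Aim 2 can be formally claimed only if the primary succeeds.
- Under the split each test loses power. For a two-arm comparison with 24 per arm (two-sided, normal approximation), the difference detectable with 80% power is √(2/24) × (z for the level + 0.842): 0.809 SD at 0.05, 0.926 SD at 0.018 and 0.934 SD at 0.0167. At a true difference of 0.809 SD, power falls from 80% at 0.05 to Φ(0.809 × √12 − 2.394) = 66% at 0.0167.
- For the same reason 0.018 should not be imposed on a single primary: it would cost power with no multiplicity to correct.

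### The between-arm test of parcel maps names no visit and gives the week-0 scan no role, although each participant is scanned at weeks 0, 2 and 4; the BNC t-tests share the gap

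*Combined protocol and SAP*

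**What the plan says.** Section 7c prepares the maps first: "the participant-specific sensory and motor brain parcels will be converted to z values". It then names the test: "The brain parcels will be combined in a second-level random effects analysis using a two sample t-test in SPM8". Voxels that differ between arms are declared at "a liberal voxel-wise p value of 0.01 and a cluster-level p value of 0.05 corrected for multiple comparisons". None of these sentences says which scan supplies the map, whether a difference between scans is formed, or whether the week-0 map enters as a covariate. The BNC comparison in the same paragraph has the same form: two-sample t-tests on Fisher-transformed correlations with a false discovery rate correction, and no visit named.

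MRI takes place "at the beginning (prior to cycling sessions) and at the end of the 2nd and 4th weeks of the intervention program" (section 4, study design). Section 7a lists rsfMRI parcels as a primary outcome at all three time points and says of them: "The parcels' center of mass, spatial maps, average and variance of the BOLD signal time courses within the parcels can be used". The trial's aim in section 4 is "to determine if the amount of changes in brain functional connectivity outcome measures (i.e., between network connectivity) is significantly different between the group" given FES cycling and the group given passive cycling.

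No other section fills the gap:
- The optional confounds in section 7b are cycling parameters, age, sex, handedness and time since injury. Baseline imaging is not among them.
- Aim 2 in section 2 uses change, but for correlating BNC with ISNCSCI, not for comparing arms.
- The intra-class correlation analysis at the end of section 7c concerns reproducibility.
- Where section 7c does intend particular visits, as in the regression of week-4 ISNCSCI on week-2 BNC, it names them.

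**The concern.** The between-arm test of a primary outcome has no defined input image. Several inputs fit the wording: a single map from any of three visits, a difference from week 0 at week 2 or week 4, or an average. They do not answer the same question and do not have the same precision. The cluster-level correction works within one map test, so it gives no protection if the input is chosen after the maps have been seen.

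Baseline is also likely to be informative. Section 5 admits ASIA grades A to D, and the pilot in section 7c found a cross-sectional connectivity measure associated with impairment (R² = 0.35). A single follow-up map can therefore be expected to carry stable differences between patients as well as any effect of cycling. The week-0 scan is the natural means of removing that variation. It is already acquired, and the plan does not use it in this test.

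**Working it through.** **Inputs from the documents:** 24 per arm, randomized (section 4); three scans per participant (section 4); alpha 0.018, 80% power, 24 subjects, R² = 0.35 from 12 patients (section 7c); voxel-wise p of 0.01 (section 7c). **Assumed:** the between-visit correlation rho, equal SD at each visit, and one scalar summary per participant such as mean z within a parcel. The documents give no rho, and section 7c says the variability of BNC in response to FES is not yet known.

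**1. The plan's own figure.** |r| = sqrt(0.35) = 0.592 and atanh(r) = 0.6801. For a correlation test, n = ((z_alpha + z_power)/atanh(r))² + 3.
- Two-sided: ((2.3656 + 0.8416)/0.6801)² + 3 = 25.2, so 26.
- One-sided: ((2.0969 + 0.8416)/0.6801)² + 3 = 21.7, so 22.
- A two-sided noncentral-t calculation for a regression slope gives 23.

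The stated 24 fits a single-correlation calculation, although the plan does not say which pilot figure was used. It is not a between-arm calculation and does not settle the present point.

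**2. Chance imbalance at week 0.** SE of the arm difference = sqrt(2/24) = 0.289 SD. P(|difference| > 0.3 SD): 0.3/0.289 = 1.04, which gives 30%. P(|difference| > 0.5 SD): 0.5/0.289 = 1.73, which gives 8%. An imbalance carries into an unadjusted follow-up comparison as rho times its size: 0.3 × 0.3 = 0.09 SD at rho 0.3, and 0.7 × 0.3 = 0.21 SD at rho 0.7.

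**3. Variance relative to a single follow-up visit.** The change score has 2(1-rho) and the baseline-adjusted value 1-rho².

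| rho (assumed) | change score | baseline-adjusted |
|---|---|---|
| 0.3 | 140% | 91% |
| 0.4 | 120% | 84% |
| 0.5 | 100% | 75% |
| 0.7 | 60% | 51% |
| 0.8 | 40% | 36% |

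**4. What that means for power.** Take the difference that a single-visit t-test detects with 80% power at two-sided alpha 0.018: d = (2.3656 + 0.8416) × 0.2887 = 0.926 SD. This is the normal approximation; the exact t calculation gives 77%. With variance factor f from step 3, power = Φ(3.2072/sqrt(f) - 2.3656).

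| rho (assumed) | single visit | change score | baseline-adjusted |
|---|---|---|---|
| 0.3 | 80% | 63.5% | 84.0% |
| 0.5 | 80% | 80.0% | 91.0% |
| 0.7 | 80% | 96.2% | 98.3% |

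**5. Inputs that would do harm.**
- *Week-0 maps:* the expected arm difference is zero under randomization, so the effect is missed.
- *Average of all three visits, with the full effect at weeks 2 and 4:* effect 2d/3, variance (1+2rho)/3. Power is 71%, 60% and 51% at rho 0.3, 0.5 and 0.7.
- *All three scans entered as if from different people:* the true variance is (1+2rho) times the assumed one. A nominal 0.01 voxel test has a true level of 0.042, 0.069 and 0.096 at the same rho values.

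**The case against.** The strongest reply is that the plan leaves the input unstated, which is not the same as choosing a wrong one. A reader might infer that the map test cannot test change. The documents do not support that: a two-sample t-test on participant difference maps would fit the wording and would test change directly. A reader might also infer that a single-visit comparison is biased by pre-existing injury differences. Section 4 randomizes 24 against 24, so a week-2 or week-4 comparison estimates the arm effect without bias in expectation, and the 30% and 8% figures describe ordinary chance variation that the t-test's standard error already reflects. A third inference, that three scans per person will be treated as independent, is also not in the plan. Participant-specific maps in a second-level random effects analysis point to the participant as the unit.

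It is also fair to say that the design statement names change in BNC, not in maps, so the mismatch is most direct for the BNC t-tests. Difference maps are no safe default either: below rho 0.5 they lose precision, and they require parcels that correspond across visits, when longitudinal reproducibility is itself something the study has yet to assess.

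All of this stands and limits the point. What it leaves untouched is that no section names the visit or gives the week-0 scan a role in either between-arm test. The appeal to randomization also applies to the groups as randomized. Section 4 excludes people who fail the cycling trial after they have been assigned to an arm, and allows removal for missed sessions. Baseline adjustment would not fully cure selection arising there, but it is more robust than ignoring week 0.

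**Conclusion.** The point holds as a gap with a concrete remedy, not as an invalid test. The between-arm map comparison has no stated visit and makes no use of the week-0 scan, for an outcome listed as primary at three visits in a trial interested in change. If a follow-up map is used, the cost is lost precision and unadjusted chance imbalance (SE 0.29 SD). Baseline adjustment would leave 91% to 36% of the single-visit variance over rho 0.3 to 0.8, and apart from one degree of freedom it never leaves more than 100%. A week-0 or pooled-visit map would miss or dilute the effect. The BNC t-tests have the same gap. The sizes rest on an assumed between-visit correlation, equal SD across visits and a single scalar summary; the finding that the visit and baseline handling are unstated does not depend on them.

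**What to change.** Add to section 7c, for the parcel-map and BNC comparisons alike:
1. Each participant contributes one image, or one BNC value per network pair, to any two-sample test.
2. The follow-up visit is named (week 2, week 4 or both), and the sponsor designates which is primary.
3. The main analysis is baseline-adjusted: follow-up value by arm with the week-0 value as covariate. For maps, use mean z within the parcel, or voxel-wise values where the software allows. For BNC, use the Fisher-transformed correlation.
4. If difference maps (follow-up minus week 0) are used for the voxel-wise SPM test, say that they are less precise than a single-visit map when the between-visit correlation is below 0.5 (120% of the variance at 0.4), and derive the parcels so that they correspond across visits.

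The interim look at the first 24 participants, already planned, could report the between-visit correlation pooled over arms and so replace the assumption used here.

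The cost is SAP wording, a covariate in the model and, for difference maps, a subtraction step plus the work of matching parcels across visits. No new scans or participants are needed. The wording should be fixed before any map is compared by arm.
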